### 9.5.1. Safety Analyses

For safety variables, 2 observation periods are defined:

- The pretreatment period is defined as the time from signing the ICF until administration of the first dose of study drug.

- The treatment-emergent period is defined as the time from administration of the first dose of study drug to the end of the study.

Treatment-emergent AEs are defined as those that are not present at start of study drug dosing or that represent the exacerbation of a pre-existing condition during the treatment-emergent period.

AEs will be coded using the Medical Dictionary for Regulatory Activities (MedDRA) by preferred term within system organ class. The number of AEs and the number of subjects reporting AEs will be listed and summarized descriptively by body system, preferred term, severity, and causality for each treatment group. Both pretreatment and treatment-emergent AEs (events that are new in onset or aggravated in severity following treatment) will be included in all summaries. SAEs (including death) will be summarized. Treatment-emergent AEs leading to permanent treatment discontinuation will be listed and summarized by treatment group.

### **9.5.2. Treatment Exposure**

The duration of drug exposure during the study will be summarized by treatment and calculated as: (Date of last dose – date of first dose).

The number (%) of subjects randomized and exposed to drug will be presented by specific time periods for each treatment group. The time periods of interest will be specified in the statistical analysis plan.

Treatment compliance = (the number of doses of study drug taken during the exposure period)/(the number of planned study drug doses during the exposure period) × 100%.

A summary of the treatment compliance by treatment group will be provided.

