## 4. STUDY DESIGN

### 4.1. Overall Design

This is a randomized, open-label, parallel group, multiple-dose, dose-ranging, active control, Phase 2a study. The objective of the study is to assess the PD, safety and PK of different doses of MNK6106 (oral administration) vs rifaximin in subjects 18 to 80 years of age (inclusive) with hepatic cirrhosis and a history of prior episodes of HE.

Approximately 48 subjects will be randomized to meet the primary objective. Subjects may participate in the study for a total of up to approximately 6 weeks, including a screening period of up to 28 days, a treatment period of 1 week (5 days), and a final visit 1 week (7 days [+ 3 day window]) after ending study treatment.

The final visit window may be extended, due to extenuating circumstances, to 14 days after discussion with the Sponsor.

Subjects will be confined to the study center overnight during the 5-day treatment period and randomly assigned to receive 1 of 3 dose regimens of MNK6106 or the comparator rifaximin for 5 days.

Approximately 48 subjects will be 1:1:1:1 randomized to 1 of the 4 groups. Subjects will receive either 1 of the 3 MNK6106 dosing regimens (2 g three times daily, 4 g twice daily, or 4 g three times daily) or rifaximin (550 mg twice daily) taken orally for 5 days. Samples for plasma AMM levels will be drawn at screening and on Days 1, 3 and 5/ET, predose in the morning immediately before breakfast and 4 hours ( $\pm$  15 minutes) after the morning dose as well as at the final visit. Samples for plasma PAA, ORN and PAGN will be drawn prior to the first dose on Day 1 (within 15 minutes prior to the morning dose) and then prior to (within 10 minutes) and 1 hour ( $\pm$  15 minutes) after the last dose on Days 1, 3, and 5/ET. Subjects will remain in the clinic overnight during Day 5/ET and be discharged on Day 6 after the last 24 hour urine collection is completed.

---

All treatment groups will be dosed orally as follows:

- Group A: MNK6106 2 g (2 tablets), three times daily for 5 days (6 g daily dose and 30 g total dose).
- Group B: MNK6106 4 g (4 tablets), twice daily for 5 days (8 g daily dose and 40 g total dose).
- Group C: MNK6106 4 g (4 tablets), three times daily for 5 days (12 g daily dose and 60 g total dose).
- Group D: Rifaximin 550 mg tablet (1 tablet), twice daily for 5 days (1.1 g daily dose and 5.5 g total dose).

Approximately 1 week after the end of the treatment period, subjects will complete a final visit.

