**Table 2: Summary of Treatment Groups, Frequency and Dose**

Treatment	Frequency	Dose	Total Daily Dose	Total Dose (5 days)
MNK6106	tid	2 g	6 g	30 g
MNK6106	bid	4 g	8 g	40 g
MNK6106	tid	4 g	12 g	60 g
Rifaximin	bid	550 mg	1.1 g	5.5 g

Note: bid = twice daily; tid = 3 times daily.

For the 3 times daily dosing regimen, the doses will be given at 8 AM, 1 PM, and 6 PM ( $\pm 60$  minutes); for twice daily dosing, the doses will be given at 8 AM and 6 PM ( $\pm 60$  minutes). Each dose will be administered with an 8 oz glass of room temperature water, and the subject will be required to swallow the tablet whole without chewing or crushing it, and to drink all the water. The date and actual (clock) time that the subject receives the MNK6106 study drug and the dose amount administered will be recorded on the electronic case report form (eCRF). Any

---

deviations from the dosing schedule and instructions described in this protocol will also be recorded. Each subject will be closely supervised for ingesting each of the doses and the required amount of water. The entire dose must be administered within 15 minutes.

Any loss of the study drugs will be documented and reported to Mallinckrodt Clinical Supply Management, with the approximate amount lost estimated and recorded. Replacements will be made accordingly.

The study drugs will be administered under fed (30 minutes after start of meal) conditions. Lunch and dinner will be served at approximately 30 minutes prior to dosing.

After each dose, the subjects will be required to remain in an upright position for at least 2 hours after dosing. In addition, subjects will also be required to refrain from anything more than light exercise while confined at the study site.

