### **6.4. Study Treatment Compliance**

Treatment compliance will be determined by drug accountability and dosing information recorded in the eCRF.

---

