### 8.3. Treatment Period (Week 1; Day 1 to Day 5/ET) and Day 6 (Discharge)

After randomization, subjects will enter the study, and receive active treatment (1 of 3 MNK6106 dose regimens or rifaximin) for 5 days. Subjects will be confined to the study center overnight during the treatment period and discharged on Day 6. The following procedures will be carried out on Days 1, 2, 3, 4 and 5 unless otherwise stated:

- Perform a limited physical examination (Day 1 only).
- Record the subject's weight and waist circumference (Day 1 and Day 6 only).
- Record the subject's vital signs (Day 1 through Day 6).
- Record ECG (Days 1, 3 and 5/ET only) at 1 hour after the last dose ( $\pm$  15 minutes). Complete the ECG prior to the PK sample collection if the timing is the same.
- Collect blood samples for plasma AMM (to be drawn on Days 1, 3 and 5/ET only, predose in the morning immediately before breakfast and 4 hours ( $\pm$  15 minutes) after the morning dose), as well as on the day of the final visit.
- Collect a blood sample for plasma PAA, ORN and PAGN (to be drawn on Days 1, 3 and 5/ET only). A baseline sample will be drawn prior to the first dose on Day 1 (within 15 minutes prior to the morning dose) and then prior to (with 10 minutes) and 1 hour ( $\pm$  15 minutes) after the last dose on Days 1, 3, and 5/ET.
- Collect a urine sample for PAGN. For each 24-hour collection following the first dose of the day, all urine will be collected during the specified intervals, with the last collection for Day 5/ET being collected on Day 6. A baseline urine sample will also be collected predose on Day 1.
- Collect samples for chemistry, hematology, (Days 1 through 6) and urinalysis (Days 1 through 5 only).
- Record the Conn, MELD, HESA and C-P scores (Days 1 through 6).
- Perform study drug dosing.
- Record all concomitant medications/therapies (Days 1 through 6).
- Record and assess AEs/SAEs, including AESI (Days 1 through 6).

On the Day 6 visit (discharge):

If no clinical or laboratory abnormalities are observed, subjects will be discharged from the study on the morning of Day 6. The 24-hour urine collection for PAGN will be completed on Day 6 at the end of confinement.

Additional follow-up visits will be scheduled if a subject shows any clinical or laboratory abnormalities at this visit, as deemed appropriate by the investigator/designee (classified as unscheduled visits).

---

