### **9.2. Populations for Analysis**

For the purposes of analysis, the following populations are defined

- The Modified Intent-to-Treat (mITT) Population will include all randomized subjects who receive at least 1 study treatment and who contribute any postbaseline PD data to the study.
- The Safety Population will include all subjects who receive 1 or more study treatments.
- The PK population will consist of all subjects in the Safety Population with at least 1 evaluable plasma concentration following treatment with MNK6106.

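### The exposure formula in section 9.5.2 subtracts dose dates without adding a day, so a completed 5-day course is reported as 4 days and Day-1-only dosing as 0 days

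*Combined protocol and SAP*

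**What the plan says.** Section 9.5.2 defines duration of exposure as a difference of two calendar dates, "summarized by treatment and calculated as: (Date of last dose – date of first dose". It adds no day, uses no clock time and states no unit. The same section leaves one item to a later document: "The time periods of interest will be specified in the statistical analysis plan". That concerns the reporting categories, not the duration formula.

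Elsewhere the course is described as 5 days:

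- Section 8.3 covers Day 1 to Day 5, with discharge on Day 6, and says that subjects "receive active treatment (1 of 3 MNK6106 dose regimens or rifaximin) for 5 days".
- Section 4.1 gives doses on the same basis, for example "Group A: MNK6106 2 g (2 tablets), three times daily for 5 days (6 g daily dose and 30 g total dose".
- Table 2 heads its last column "Total Dose (5 days".
- Table 1 marks study drug dosing on each of Days 1, 2, 3, 4 and 5.

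**The concern.** A duration meant to describe a course given on five consecutive days should come out as 5 for a subject who took all of it. A plain subtraction of dates counts the intervals between days, not the days, and so loses one. In a long trial nobody would notice. Here the course is so short that one day is a fifth of it, and the relative loss grows for anyone who stops early.

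Early stopping is foreseen: section 7.1 lists reasons for mandatory discontinuation, and section 9.1 says that such subjects are not replaced. A subject who took every Day 1 dose and then stopped would be listed with 0 days of exposure. That subject would still be in the Safety Population, since "The Safety Population will include all subjects who receive 1 or more study treatments". Safety and tolerability is a secondary objective (section 3.2), and the exposure table is what readers set beside the adverse events. It should agree with the course that the rest of the protocol describes.

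**Working it through.** **Inputs.** Formula: section 9.5.2. Dosing days 1 to 5: Table 1 and section 8.3. Daily and total doses: section 4.1 and Table 2. Dose times: section 6.1, which says "For the 3 times daily dosing regimen, the doses will be given at 8 AM, 1 PM, and 6 PM" and, for twice-daily dosing, gives 8 AM and 6 PM, each with a 60-minute window either way. Number randomized: 48, allocated 1:1:1:1, so 12 per arm (section 9.1).

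**Step 1: reproduce the protocol's 5 days.** Total dose divided by daily dose:

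- Group A: 30 / 6 = 5
- Group B: 40 / 8 = 5
- Group C: 60 / 12 = 5
- Group D: 5.5 / 1.1 = 5

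All four arms give 5, so the protocol counts Day 1 and Day 5 both as treatment days.

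**Step 2: apply the formula as written, and with one day added.**

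| Day of last dose | As written (last − first) | With + 1 | Shortfall against inclusive days |
|---|---|---|---|
| 1 | 0 | 1 | 1/1 = 100% |
| 2 | 1 | 2 | 1/2 = 50% |
| 3 | 2 | 3 | 1/3 = 33% |
| 4 | 3 | 4 | 1/4 = 25% |
| 5 | 4 | 5 | 1/5 = 20% |

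The formula as written does not return 5 for a completed course. With the added day it does.

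**Step 3: total over the trial if all 48 complete.** Inclusive days: 48 × 5 = 240. As written: 48 × 4 = 192. Shortfall: 48 subject-days, and 48 / 240 = 20%. Per arm of 12: 60 against 48. If some subjects stop early, the shortfall is still exactly 1 day per treated subject, but it is a larger share of a smaller total.

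**Step 4: try an elapsed-time reading.** From 8 AM on Day 1 to 6 PM on Day 5 is 4 × 24 + 10 = 106 hours, and 106 / 24 = 4.42 days (104 to 108 hours with the windows). For all Day 1 doses and nothing more, 8 AM to 6 PM is 10 hours, or 0.42 days (8 to 12 hours with the windows). Neither pair matches the formula's 4 and 0.

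**Step 5: what does not move.** For two arms with true mean durations a and b, the formula gives (a − 1) − (b − 1) = a − b, so the difference is unchanged.

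**The case against.** The best defence is that section 9.5.2 never claims to count dosing days. It defines a difference between two dates, and such a difference is a legitimate quantity. On an elapsed-time view the formula is even slightly closer than the proposed replacement: 4 is 0.42 day below 4.42 (about 9% low), while 5 is 0.58 day above it (about 13% high).

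Part of this stands. The statements that each duration is 1 day short, and that the total is 20% low, hold only under inclusive calendar-day counting. But the text subtracts dates and does not use clock times, so it does not define elapsed time. The inclusive count is also the one behind the protocol's own 5 days. And a subject who took all Day 1 doses has 10 hours between first and last dose, so 0 fails on the elapsed reading as well.

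Another possible objection is that an inclusive count would overstate exposure if dosing were interrupted. Section 7.1 permits no temporary discontinuation, so for a subject treated as planned the inclusive count equals the number of dosing days.

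Two stronger readings are tempting, and the documents do not support either.

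- A reader might infer that the compliance percentage is also wrong. If the planned doses were taken over 4 days, a fully compliant subject would score 15/12 or 10/8, that is 125%. But the compliance formula does not say that its exposure period is the computed duration. Read as first to last dosing day, it gives 15/15 or 10/10 for a completer. No error is shown there.
- A reader might infer that completers would fall out of a 5-day exposure category. No such category appears in the documents. The categories are left to a statistical analysis plan that is not part of the text reviewed.

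**Conclusion.** The formula as written gives a wrong reported number: 4 days for a completed 5-day course, and 0 days for a subject treated only on Day 1. Nothing else in the document corrects it. Whether a later analysis plan adds the day cannot be checked from this text.

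The size is 1 day per treated subject: 20% if all 48 complete, and proportionally more for early stoppers. These figures assume inclusive calendar-day counting.

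The effect is limited to the descriptive exposure table. Differences between arms in mean duration are unchanged. The ammonia endpoint does not use the duration. Safety Population membership depends on receiving a treatment, not on how long. The study is exploratory, with no hypothesis to test (section 9.3). The point is minor, and the arithmetic behind it is not in doubt.

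**What to change.** In section 9.5.2, define duration of exposure (days) = date of last dose − date of first dose + 1, and state the unit. Repeat the same formula in the statistical analysis plan so that the two agree.

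The cost is one added term. The calculation uses the two dates that the present formula already needs, and section 6.4 confirms that dosing data are captured: "Treatment compliance will be determined by drug accountability and dosing information recorded in the eCRF". No new field, visit, sample or change in sample size follows. Section 10.1.1 requires an amendment for any change in the study plan, so the edit can go in with the next one.

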### **9.5.3. Interim Analyses**

No interim analyses are planned for this study.

### **9.5.4. Handling Missing Data**

There is no imputation for missing PD data.

## **10. SUPPORTING DOCUMENTATION AND OPERATIONAL CONSIDERATIONS**

### **10.1. Regulatory, Ethical, and Study Oversight Considerations**

#### **10.1.1. Regulatory and Ethical Considerations**

The study will be conducted in full compliance with applicable international, national and local regulatory requirements; FDA regulations including 21 CFR 314.106 and 312.120, (where applicable), ICH guidelines for Good Clinical Practice (GCP), in accordance with the ethical principles that have their origins in the Declaration of Helsinki, and European regulation 536/2014/EU (where applicable).

It is the responsibility of the investigator to obtain the approval of the IRB/IEC before the start of the study. A copy of the approval letter along with a roster of IRB/IEC members and compliance letter and/or the US Department of Health and Human Services general assurance number (if applicable) will be provided to the sponsor and retained as part of the study records. During the course of the study, the investigator will provide timely and accurate reports to the IRB/IEC on the progress of the study at appropriate intervals (not to exceed 1 year) and at the completion of the study. The investigator will notify the IRB/IEC of SAEs or other significant safety findings per IRB/IEC guidelines. The study protocol, ICF, advertisements (if any), and amendments (if any) will be approved by the IRB/IEC in conformance with international, national and local regulatory requirements.

Any change in the study plan requires a protocol amendment. An investigator must not make any changes to the study without IRB/IEC and sponsor approval except when necessary to eliminate apparent immediate hazards to the subjects. A protocol change intended to eliminate an apparent immediate hazard to subjects may be implemented immediately, but the change must then be documented in an amendment, reported to the IRB/IEC within 5 working days, and submitted to the appropriate regulatory agency in the required time frame, if appropriate.

#### **10.1.2. Financial Disclosure**

Investigators and subinvestigators will provide the sponsor with sufficient, accurate financial information as requested to the sponsor to submit complete and accurate financial certification or disclosure statements to the appropriate regulatory authorities. Investigators are responsible for providing information on financial interests during the course of the study and for 1 year after the end of the study.

#### **10.1.3. Subject Information and Consent**

The ICF must be approved by the sponsor and the IRB/IEC before any subject provides consent. The investigator will provide Mallinckrodt with a copy of the IRB/IEC-approved ICF and a copy of the IRB/IEC's written approval before the start of the study.

At screening (and at other times as may be required by the study or when changes are made to the consent form), subjects will read the consent form(s) and any privacy authorization as required by local and national regulations (such as the Health Insurance Portability and Accountability Act [HIPAA] authorization form), if applicable after being given an explanation of the study. Before signing the consent form(s) and the privacy authorization form (if applicable), subjects will have an opportunity to discuss the contents of these forms with study site personnel.

Subjects must assent understanding of and voluntarily sign these forms in compliance with ICH GCP and all applicable national and international regulations, before participating in any study-related procedures. Subjects will be made aware that they may withdraw from the study at any time. Subjects unable to give written informed consent must orally assent to the procedures and written informed consent must be obtained from a legally authorized representative in accordance with national and local laws, as applicable.

The ICF must contain all applicable elements of informed consent and the mandatory statements as defined by national and local regulations including confidentiality. All versions of each subject's signed ICF must be kept on file by the study site for possible inspection by regulatory authorities and/or authorized Mallinckrodt personnel. Signed copies of the consent form(s) and the HIPAA authorization form, if applicable, will be given to the subject.

The subjects will be made aware of their right to see and copy their records related to the study for as long as the investigator has possession of this information. If the subject withdraws consent and/or HIPAA authorization, the investigator can no longer disclose health information, unless it is needed to preserve the scientific integrity of the study.

#### **10.1.4. Data Protection**

Study subjects will be assigned a unique identifier by the sponsor or designee. Any subject records or datasets that are transferred to the sponsor will contain the identifier only; subject names or any information which would make the subject identifiable will not be transferred.

The subjects must be informed that their personal study-related data will be used by the sponsor in accordance with local data protection law. The level of disclosure (in accordance with local and/or national law) must also be explained to the subject.

The subjects must be informed that their medical records may be examined by Clinical Quality Assurance auditors or other authorized personnel appointed by the sponsor, by appropriate IRB/IEC members, and by inspectors from regulatory authorities.

#### **10.1.5. Dissemination of Clinical Study Data**

Aggregate results data will be provided to the study sites that actively enrolled subjects into this study after the clinical study report is finalized.

Study results and de-identified individual subject data will be released as required by local and/or national regulation.

#### **10.1.6. Data Quality Assurance**

The sponsor performs quality control and assurance checks on all clinical studies that it sponsors. Before enrolling any subjects in this study, sponsor personnel and the investigator review the protocol, the Investigator's Brochure, the eCRF and instructions for their completion, the procedure for obtaining informed consent, and the procedure for reporting AEs and SAEs. A qualified representative of the sponsor will monitor the conduct of the study.

The investigator will permit study-related monitoring, audits, IRB/IEC review, and regulatory inspections by providing direct access to original source data and documents.

Each subject's eCRF should be fully completed and submitted to the sponsor in a timely fashion.

If an investigator retires, relocates, or otherwise withdraws from conducting the study, the investigator must notify the sponsor to agree upon an acceptable storage solution. Regulatory agencies will be notified with the appropriate documentation.

---

Any significant changes in study personnel will require an updated statement of investigator (ie, FDA Form 1572) to be filed with the sponsor.

The investigator must notify their IRB/IEC of protocol deviations in accordance with local regulatory and IRB/IEC requirements.

The eCRF data are stored in a database and processed electronically. The sponsor's MM reviews the data for safety information. The data are reviewed for completeness, and logical consistency. Automated validation programs will identify missing data, out-of-range data, and other data inconsistencies. In addition, clinical laboratory data will be processed electronically. Requests for data clarification are forwarded to the study site for resolution.

